### **Potential Risks to Participants**

Information on potential risks to patients participating in this study is as follows:

- *Oral Examinations/Head and Neck Examination:*

The oral examination will involve procedures that are routinely performed in dental practice. A licensed dentist/hygienist will perform the procedures. The risks from the oral examination include minor discomfort or minor pain during the procedures.

- *Biological Sample Collection:*

Urine (if female of child bearing potential) will be collected. This collection processes minimal risk to the patient.

- *Blood Sampling Collection:*

Peripheral blood sampling will be performed by a trained phlebotomist, nurse, dentist or physician utilizing standard venipuncture techniques. Patients may have some discomfort and/or bruising at the site of needle entry. There is a very small risk of fainting. Infection in the area of the needle insertion is rare. Preventive measures will be used during sample collection to reduce the risk of these rare side effects.

- *GDC-0449 Administration:*

Vismodegib is a previously studied drug. Our knowledge of adverse events related to vismodegib results from clinical trials. Adverse reactions and the associated incidence related to vismodegib are documented. Participants will be closely monitored for previously-reported and unrecognized adverse events. Tumor growth in participants on the drug is possible; however, participants will be monitored with both clinical and radiographic examination to identify such growth. Participants on vismodegib might avoid surgery and the morbidity (*i.e.*, loss of bone and teeth) associated with surgery.

GDC-0449 (Vismodegib) capsule is a Hh pathway inhibitor indicated for the treatment of adults with metastatic basal cell carcinoma, or with locally advanced basal cell carcinoma that has recurred following surgery or who are not candidates for radiation.

The most common adverse reactions (incidence  $\geq 10\%$ ) are muscle spasms, alopecia, dysgeusia, weight loss, fatigue, nausea, diarrhea, decreased appetite, constipation, arthralgias, vomiting and ageusia. In clinical trials, a total of 3 of 10 pre-menopausal women developed amenorrhea while receiving GDC-0449. Treatment-emergent Grade 3 laboratory abnormalities observed in clinical trials were hyponatremia in 6 patients (4%), hypokalemia in 2 patients (1%), and azotemia in 3 patients (2%).

The safety and efficacy of vismodegib in pediatric patients has not been established. Studies in animals indicate that oral Hh pathway inhibitors pose a substantial risk of developmental defects during the post-natal period, which includes irreversible effects on growing teeth or bones and male reproductive organs. The occurrence of premature epiphyseal fusion has been identified on routine pharmacovigilance through literature review and from serious adverse events (SAEs) reported in an Investigator Sponsored Trial (IST) of pediatric patients receiving vismodegib therapy. In some cases, fusion progressed after drug discontinuation.

In this study, the safety and efficacy of oral GDC-0449 in the management of NBCCS-associated KCOT and sporadic KCOT will be examined. The recommended dose is 150mg taken orally once daily until disease progression or until unacceptable toxicity. The capsule has a pink opaque body and a grey opaque cap with "150 mg" printed on the capsule body and "Vismo" printed on the capsule cap in black ink. It can be taken

with or without food and capsules should not be opened or crushed. If patients miss a dose, they will be advised not to make up that dose but instead to resume dosing with the next scheduled dose.

Pregnancy status prior to the initiation of GDC-0449 will be verified with a serum pregnancy test. Male and female patients will be advised of the risks of embryo-fetal death and severe birth defects and the need for contraception during and after treatment.

In addition, patients must agree not to donate blood or blood products during the study and for 24 months after discontinuation of vismodegib.

If a patient experiences unacceptable drug toxicity, he/she will be allowed a treatment break lasting for at least one month, up to three months. If the patient is unable to resume treatment after an 3 month treatment break, he/she will be discontinued from the study.

A potential risk of treatment of KCOT with vismodegib is disease progression, *i.e.* tumor growth. Participants will be closely monitored with clinical and radiographic examination for evidence of disease progression. The natural history of KCOTs is that the tumors grow and expand slowly relative to the proposed examination schedule. Therefore, it is highly unlikely that unanticipated growth in participants on vismodegib would be encountered.

The potential benefit of treatment of KCOT with vismodegib is decreased tumor recurrence and reduced surgical morbidity. Currently the management of KCOT is surgical. The surgical options include: 1. resection, 2. enucleation with or without treatment of the bony cavity using tissue fixatives or liquid nitrogen, or 3. surgical decompression. The morbidity of surgical resection and enucleation involves the loss of bone and teeth. In some cases the sensory nerve in the proximity of the tumor is removed leaving the patient with paresthetia or anesthesia in the distribution of the face or tongue. Replacement of bone and teeth is extremely difficult and in many cases not possible. Decompression involves placement of a drain into the tumor cavity followed by irrigation of the bony cavity three times a day for 12 to 24 months. Often after this treatment eventual removal of the tumor is required. A potential benefit for participants treated with vismodegib is that they might avoid the morbidity associated with the above-described surgery.

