### **Do not open or crush capsules**

**If a dose of vismodegib is missed, do not make up that dose; resume dosing with the next scheduled dose.**

### **Vismodegib Dose and Schedule Modifications**

Vismodegib dose modifications and schedule modifications during the study are not recommended due to the pharmacokinetic characteristics of the drug (see Vismodegib Investigator Brochure v10, Section 5.9.3). Briefly, vismodegib's pharmacokinetic profile is a result of high affinity, reversible binding to Alpha-1 acid Glycoprotein (AAG) and binding to albumin, in addition to solubility limited absorption and slow metabolic elimination properties[24]. Initiation of less frequent administration schedules than the approved dose and schedule of vismodegib of 150 mg orally once daily, (i.e. 150 mg three times weekly [TIW] or 150 mg once weekly dosing), was associated with marked decrease in the pharmacologically active unbound fraction. Unbound steady-state vismodegib concentrations were 60% and 85% lower for the TIW and QW dose groups, respectively, relative to the QD dose group [25, 26]. Such decreases may be associated with loss of vismodegib activity based on findings from nonclinical models. Integrated PK/pharmacodynamic modeling of vismodegib in xenograft models has revealed a steep relationship between pathway modulation (GLI1 inhibition) and anti-tumor effect, suggesting that even small reductions in exposure could lead to dramatic loss in vismodegib activity (see Vismodegib Investigator's Brochure v10, Section 4.1.2.8)

Dose reduction of vismodegib is not permitted as there is only a 150-mg capsule strength available. Capsules should not be opened or crushed. If a treatment interruption occurs, and it is determined that vismodegib will be re-started, the original dose will be maintained

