  - Once the baseline visit assessments are complete and eligibility is confirmed, all patients will receive the same treatment (150 mg/day of GDC-0449 orally for 1 year). After the first study drug administration, patients will be observed and monitored by the investigator for 6 hours. Patients will maintain the medication regimen until they are required to discontinue the study drug due to disease progression, or unacceptable toxicity, as assessed by the investigator.
- Study Drug Dispense until next visit
- Adverse Events

Upon discharge from the clinic, specific instructions will be given to patients regarding the use of the medication, as well as adequate study drug supplies until their next visit. Patients will be instructed the following:

- Not to donate blood or blood products while receiving GDC-0449 and for at least 24 months after the last dose of the study drug.
- Not to get pregnant during the study and for 24 months after the last dose of the drug (see more details in Appendix 2)
- To take 150 mg of GDC-0449 orally once daily with or without food and to swallow capsules whole. Capsules should not be opened or crushed.

- If a dose is missed, not to make up that dose but to resume dosing with the next scheduled dose.
- To notify the investigator immediately if they notice any changes with their health status or if they become pregnant.

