#### **4.5 Discontinuation of Protocol-Specified Therapy**

No dose reductions will be allowed in this study. Treatment with vismodegib may only be interrupted for up to:

- Two consecutive weeks if a patient becomes temporarily unable to swallow capsules
  
- Two consecutive weeks in case of an intolerable toxicity finding

A total up to eight weeks of dose interruptions (e.g., 4 x 2-week interruptions, 8 x 1-week interruptions, etc.) is allowed during the Treatment Phase.

Protocol-specified therapy may be discontinued for any of the following reasons:

- Progressive disease (PD)
  
- Unacceptable toxicity
  
- Patient election to discontinue therapy (for any reason)
  
- Physician's judgment

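### The protocol gives two toxicity-break rules that no single break can satisfy and, as a separate matter, conflicting post-treatment contraception periods for women and for men

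*Combined protocol and SAP*

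**What the plan says.** **Toxicity breaks.** The text under Potential Risks to Participants (Section 4.4) says that a patient with unacceptable drug toxicity, in its words, "he/she will be allowed a treatment break lasting for at least one month, up to three months". It continues: "If the patient is unable to resume treatment after an 3 month treatment break, he/she will be discontinued from the study".

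Section 4.5 sets a different limit. It opens with "Treatment with vismodegib may only be interrupted for up to" and then lists, for toxicity, "Two consecutive weeks in case of an intolerable toxicity finding". It adds a cap for the treatment phase: "A total up to eight weeks of dose interruptions". The same section lists unacceptable toxicity under "Protocol-specified therapy may be discontinued for any of the following reasons".

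Other places bear on what happens next:
- Section 4.2 says "Dose reduction of vismodegib is not permitted as there is only a 150-mg capsule strength available", and that a patient who restarts does so at the original dose. It gives no length for an interruption.
- Section 4.4.2 has patients take the drug "until they are required to discontinue the study drug due to disease progression, or unacceptable toxicity, as assessed by the investigator".
- The continuance criteria in Section 4.4.3 release patients with unacceptable toxicity from the study. Section 4.6 says only that they may be discontinued from it.

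**Contraception after treatment.** For women, Sections 4.1.1 and 4.4.2 require 24 months. The exclusion criteria, the visit instructions in Sections 4.4.2 to 4.4.4 and the pregnancy-reporting rule in Section 5.3(e) also use 24 months, for avoiding or reporting pregnancy. Appendix B says 9 months. For men, Section 4.4.2 asks for condom use for 2 months after the last dose, while Section 4.1.1 says 3 months. Section 5.3(e) uses a 3-month window for reporting a partner's pregnancy. The discharge instructions in Section 4.4.2 also point to an Appendix 2, which does not exist; Appendix B is meant.

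**The concern.** An investigator facing toxicity has few options. Dose reduction is barred, so an interruption is the only dosing response short of stopping. If the two interruption rules exclude each other, whether the patient pauses, stops drug or leaves the study depends on which section is read.

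The situation is foreseeable. In the Gorlin syndrome trial summarised in Section 1.3, 14 of 26 vismodegib patients (54%) stopped drug because of adverse events. In the large safety study in the same section, 178 of 500 (35.6%) did. Those rates come from other populations and do not predict a count here, but they show that the decision is unlikely to be rare.

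The contraception wording matters for a different reason. The protocol names embryo-fetal death and severe birth defects as risks of the drug. A duration shorter than the eligibility criterion is a safety-text error even if few people would follow it.

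**Working it through.** The plan states no figure to reproduce. The check sets the stated durations side by side.

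**Break rules.** Inputs: the risk section allows 1 to 3 months; Section 4.5 allows at most 2 weeks at a time and 8 weeks in total. Conversions:
- 1 month = 365/12 = 30.4 days (28 to 31 by calendar); 3 months = 3 × 30.4 ≈ 91 days.
- 2 weeks = 2 × 7 = 14 days; 8 weeks = 8 × 7 = 56 days.

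The minimum under the risk section divided by the single maximum under Section 4.5 is 30.4/14 = 2.17, with a range from 28/14 = 2.0 to 31/14 = 2.2. The permitted ranges do not overlap whatever length of month is used.

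| Length of one break | Risk section | Section 4.5 |
|---|---|---|
| 1 to 14 days | too short | allowed |
| 15 to about 29 days | too short | over the single limit |
| about 30 to 56 days | allowed | over the single limit |
| 57 to about 91 days | allowed | over both limits |

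A full three-month break exceeds the total cap by 91 − 56 = 35 days.

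**Do the two rules have different triggers?** The risk section speaks of unacceptable toxicity, Section 4.5 of intolerable toxicity. Neither term is defined. The restrictive opening of Section 4.5 governs interruptions in general, and that section treats unacceptable toxicity as a ground for stopping therapy. Sections 4.4.2 and 4.4.3 likewise treat it as a reason to stop drug or be released. Separating the triggers therefore leaves the same patient with a break of up to three months in one place and a stop or release in others.

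**Contraception.** Women: 24 − 9 = 15 months' difference. Men: 3 − 2 = 1 month. Sections 4.4.4 and Appendix A place post-treatment pregnancy tests at months 1, 2, 3, 7, 12 and 24. Only those at months 12 and 24 fall after month 9, so 2 of 6 cover the 15 months that Appendix B would leave out. A test detects a pregnancy; it does not prevent one.

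**The case against.** The strongest reply on the break rules is that Section 4.5 is plainly the operative text. It is the dedicated section, its wording is exclusive and it gives worked examples, whereas the other rule sits in a narrative about risks. Most investigators would turn to Section 4.5. That stands as a reason to moderate the rating. It does not remove the conflict, because the risk section is itself written as a rule with a consequence and nothing gives Section 4.5 precedence.

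A reader might infer that the protocol leaves no way to manage a patient whose toxicity outlasts the limits. The documents do not support that. Section 4.5 lists unacceptable toxicity and physician's judgment as grounds for stopping therapy, so a route exists. What is missing is a statement tying it to the limits.

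On women's contraception, the reply is also strong. Sections 4.4.2 to 4.4.4 print 24 months beside their references to Appendix B, and Section 4.4.2 sends the reader there for definitions and acceptable methods, not for a duration. Eligibility requires agreement to 24 months. Appendix B also carries text about girls before menarche, which does not fit an adults-only trial, so the 9 months looks like a stray line. It would be wrong to infer that women in this trial will generally be told 9 months.

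For men, the 3 months in Section 4.1.1 comes after the clause on advising partners. Attaching it to the man's own condom use as well is the natural reading, but it is a reading. Section 5.3(e) is a reporting window and supports the 3 months only indirectly.

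**Conclusion.** There are two separate wording conflicts, each of which should be fixed on participant-safety grounds.

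First, no single toxicity break satisfies both the risk section and Section 4.5, and no text says which governs. The minimum under one is 2.0 to 2.2 times the single maximum under the other.

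Second, Appendix B is 15 months shorter for women than the eligibility criterion, and Section 4.4.2 is 1 month shorter for men. The risk for women is limited by the consistent 24-month wording elsewhere.

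The conclusion rests on a literal reading of the durations and, for men, on taking the 3 months to cover condom use. A reader might go further and infer that the conflicts distort the tumour-volume result or must be resolved before the trial can be interpreted. The documents give no basis for that: neither the number of patients affected nor any effect on the primary result can be computed from them. Nor do they show what participants are told in the consent form, which was not available for this review.

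**What to change.** **Break rules.**
- Make Section 4.5 the single interruption rule. Its exclusive wording suits that role. So does the warning in Section 4.2, drawn from xenograft modelling, that even a small loss of exposure could cost much of the drug's activity.
- Delete the two break sentences under Potential Risks to Participants and refer to Section 4.5 instead.
- Have the sponsor confirm the single and total limits, and state in Section 4.5 that exceeding them means stopping study drug.
- If such patients are to stay on the existing visit and CT schedule, reword the toxicity item in the Section 4.4.3 lists and in Section 4.6 so that it means stopping drug, not leaving the study. A cross-reference alone would leave Section 4.4.3 releasing the patients whom Section 4.5 keeps. The same item recurs in the post-treatment lists in Section 4.4.4. No drug is taken then, so the interruption rule has no bearing, but the line should not be left to release a patient who stopped drug earlier.

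**Contraception.** Change Appendix B to 24 months and the condom period in Section 4.4.2 to 3 months. Correct the Appendix 2 pointer in Section 4.4.2 to Appendix B. Check that the consent form agrees.

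**Cost.** Amendment wording, sponsor confirmation and one consent-form check. Nothing is added to the schedule in Appendix A. Patients who stop drug but stay on study would keep visits and scans that are already planned.

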#### **4.4.1 Phase 1: Screening**

Potential patients (10 with NBCCS-associated KCOT and 10 with sporadic KCOT, males and females,  $\geq 18$  years) will be recruited from the Department of Oral and Maxillofacial Surgery at NYU College of Dentistry, NYU Langone Medical Center and Bellevue Hospital, as all these institutions represent major referral sources for head and neck pathology. Patients will also be recruited from other private and academic oral and maxillofacial surgery practices both in the New York area and other parts of the country

by referral. Investigator will present this study during society meetings so that other surgeons can refer KCOT patients to this study.

Before a patient's participation in the study, the investigator will be responsible for obtaining written ICF from the patient, after adequate explanation of the aims, methods, anticipated benefits and potential risks of the study and before any protocol specific screening procedure is performed or the study drug is administered. The patient will be given ample time to consider the information provided and ask questions before giving written consent.

The acquisition of informed consent will be thoroughly documented in the patient's chart and the informed consent form will be personally signed and dated by both the patient and the person who conducted the informed consent discussion. A patient will be considered enrolled in the study, once the informed consent form is signed. The original informed consent will be retained and a copy will be provided to the patient. The same process will be followed for the consenting for optional future genetic testing on blood and on the tumor.

#### **4.4.2 Baseline Visit**

The following procedures will be performed at Baseline visit (study procedures and assessments during the baseline visit can be conducted over several visits until all inclusion/exclusion criteria are verified and patient is eligible to proceed with treatment (first study drug administration)).

After obtaining written Informed Consent for a potential subject, a unique Screening number will be assigned and the following evaluations will be performed to screen for eligibility:

- Informed Consent and Screening
- Review of Inclusion/Exclusion Criteria
- Review of Medical Records, if applicable
- Medical/Dental History
- Concomitant Medications
  - All prescription, non-prescription medicines, vitamins and herbal supplements will be recorded at the baseline visit in the concomitant medication CRF. Throughout the study, any changes in concomitant medication must be recorded by the investigator.
- Demographics (including height and weight)
  - In addition to the height and weight, the following information will be collected: date of birth, gender and race.

- Serum Pregnancy Test (if female patient of child bearing potential):
  - Female patients of reproductive potential are required to use two forms of acceptable contraception during therapy and for 24 months after completing therapy. See appendix B for definition of reproductive potential and acceptable contraception. Male patients must use condoms at all times, even after a vasectomy, during sexual intercourse with female partners of reproductive potential during treatment with vismodegib and for 2 months after the last dose to avoid exposing a pregnant partner and unborn fetus to vismodegib.
  - If 7 days have passed between the patient's enrollment in the study (date the ICF was signed) and the first study drug administration, the serum pregnancy test will be repeated.
  
- Oral Cavity Assessment (soft & hard tissues, extraoral, head & neck)
  
- Physical Exam
  
- Clinical Laboratories
  - Complete blood count, serum pregnancy test, serum chemistry, coagulation time, and liver function will be assessed: white blood count, hemoglobin, platelets, glucose, uric acid, calcium, phosphorus, sodium, potassium, chloride, alkaline phosphatase, albumin, alanine transaminase (ALT), aspartate transaminase (AST), BUN and creatinine
  - All laboratory results will be reviewed and the reports will be signed by the investigator. Any results considered to be of clinical significance must be dealt with and followed up as clinically appropriate. All laboratory results considered to represent an AE must be documented in the CRF. Repeat samples will be taken if required for clinical follow up or because the sample is lost or damaged. Any abnormal end of treatment clinical laboratory result of clinical significance must be repeated at regular intervals until it returns to normal, or until the investigator is satisfied that the abnormality is not related to the study drug and needs no further investigation.
  
- Genetic Testing of blood for *PTCH1* mutation
  
- Genetic Testing of the tumor (if biopsy on excision is required for *PTCH1* mutation)
  
- Vital Signs (blood pressure, heart rate, temperature)
  
- Verification of KCOT Diagnosis
  - If a patient had an outside biopsy, then a copy of the pathology report and slides confirming the KCOT diagnosis will be obtained. For patients with multiple KCOTs associated with NBCCS, the pathology report and slides associated with each of the lesions will be obtained. If a patient has a lesion that is suspicious for KCOT, but no biopsy, then a biopsy will be performed as a standard of care. If a patient has multiple KCOTs associated with

NBCCS but there is no biopsy of any of the lesions, then a biopsy will be performed on selected lesions.

- The investigator will review the patient's medical records to confirm that the patient was treated with the standard of care and that the KCOT is recurrent.
- Biopsy of the Tumor, if applicable
- Panoramic Radiograph
- Volumetric CT Scan
  - Once the diagnosis of recurrent KCOT is confirmed a baseline volumetric CT scan will be obtained. The baseline CT will include the jaws and the brain. Patients must have at least one lesion measuring at least 1 cm in dimension to be enrolled.
- Skin Examination (for NBCCS-associated KCOT patients)
  - The entire skin will be examined and basal cell carcinomas, if present, will be mapped by location and size
- Photographs of Skin Lesions, if applicable
- Study Drug Administration – First Dose
  - Once the baseline visit assessments are complete and eligibility is confirmed, all patients will receive the same treatment (150 mg/day of GDC-0449 orally for 1 year). After the first study drug administration, patients will be observed and monitored by the investigator for 6 hours. Patients will maintain the medication regimen until they are required to discontinue the study drug due to disease progression, or unacceptable toxicity, as assessed by the investigator.
- Study Drug Dispense until next visit
- Adverse Events

Upon discharge from the clinic, specific instructions will be given to patients regarding the use of the medication, as well as adequate study drug supplies until their next visit. Patients will be instructed the following:

- Not to donate blood or blood products while receiving GDC-0449 and for at least 24 months after the last dose of the study drug.
- Not to get pregnant during the study and for 24 months after the last dose of the drug (see more details in Appendix 2)
- To take 150 mg of GDC-0449 orally once daily with or without food and to swallow capsules whole. Capsules should not be opened or crushed.

- If a dose is missed, not to make up that dose but to resume dosing with the next scheduled dose.
- To notify the investigator immediately if they notice any changes with their health status or if they become pregnant.

